9.4 Data sources

We will use the unique nationwide register-data available to us, and construct country-specific cohorts with individual-level information on dates of vaccination and dates of endpoints together with relevant covariate information. All Nordic residents are assigned a unique personal identifier at birth or immigration, enabling unambiguous linkage between registers. Thus, the data from all the Nordic countries are based on individual-level information and have full availability during the planned study period. The registers are updated daily and there is no lag time (except for the Swedish and Finnish registers, for which there is a lag of 2 to 4 weeks; we do not expect the lag time of information for these data sources to differentiate between the comparative vaccinated groups. Furthermore, given the study end is 28 February 2022, all countries are expected to have full data availability). All countries have universal and tax-financed healthcare systems and reporting to national registers is mandatory, providing near-complete follow-up of all residents over time.

In the following table, we present the data sources that will be used for the study. All data sources are nationwide registers in native format. All study subcontractors have access to their country-specific data and can link data between registers for the purpose of our study.

Data source (country)	Details of the individual-level data sources
Denmark	
The Civil Registration System (23)	The register provides the mandatory unique personal identifier for all permanent residents of Denmark, which allows linkage between all Danish health care services and civil registrations systems. The register has existed since 2 April 1968. In addition, it holds general demographic information such as birthdate and sex as well as continuously updated information and dates on historical addresses, immigration and emigration status, and death.
The Danish Vaccination Register (24)	The register holds information on all vaccinations given in Denmark including information on vaccination date, type, dose, and product batch number ever since 15 November 2015 (where reporting to the register became mandatory). Specifically related to this study, the Danish Health Agency have provided the governmentally assigned covid-19 vaccine priority groups that were prioritized groups according to the risk of severe infection as well as whether being health and social care workers.

The Danish Microbiology Database (25)	Information on positive PCR tests for SARS-CoV-2 will be drawn from The Danish Microbiology Database (MiBa) that holds information on all microbiology samples analysed at Danish departments of microbiology, including information on SARS-CoV-2 PCR test results, date of sampling, date of analysis, type of test and interpretation of test. The SARS-CoV-2
	PCR tests have been freely available to all individuals in Denmark regardless of symptoms status throughout the covid-19 pandemic.
The National Patient Register (26)	The register covers all hospital-contacts in Denmark with information on the duration of the contact, department of admission and other hospital characteristics. Treating physician-assigned diagnoses have been registered according to ICD-10 codes since 1994.
FINLAND	
The Finnish Population Information System (27)	The register is an electronic register including personal data of all permanent residents in Finland. It contains demographic information such as the unique personal identifier in Finland, date of birth, mother tongue as proxy for country of birth, place of residence, date of death, and date of immigration and emigration. The register is held by the Digital and Population Data Services Agency.
Register of Social Assistance (28)	The register holds information on individuals in long-term care and/or with need for social assistance including social rehabilitation. This assistance may be given in nursing homes, people's own homes or other institutions. The register is held by the Finnish Institute for Health and Welfare.
Social and Healthcare Professionals Register (29)	The register contains person-level data on rights to act as health care personnel.
The National Vaccination Register (30)	The register, which is based on the Register of Primary Health Care Visits, holds information on all Covid-19 vaccinations administered in Finland. Data include the date of vaccination, vaccine batch number and trade name.
National Infectious Diseases Register (31)	The register contains information on notifiable diseases which must be reported by the laboratories and the physician treating the patient, or performing an autopsy, in accordance with the Finnish Communicable Diseases Act. All laboratory-confirmed SARS-CoV-2 infections are recorded in the National Infectious Diseases Register, including the sample. The register is held by the Finnish Institute for Health and Welfare.

National Care Register for Health Care (32) Finnish Intensive Care	The register comprises information on all in-hospital care (since 1969) and outpatient specialist care (since 1998) in Finland, including admission and discharge dates, whether hospitalization was planned or acute, codes for discharge diagnoses (according to ICD-10) and surgical procedures, whether discharged as deceased, to own private residence or other health care facilities, type of department and hospital. The register is held by Finnish Institute for Health and Welfare.
Consortium's Quality Register for Intensive Care	The register records data on all patients treated in an intensive care unit in Finland.
Special Reimbursement Register and Prescription Centre database	These data collections are maintained by the Finnish Social Insurance Institution. The Special Reimbursement Register allows the identification of individuals entitled to special reimbursement for medical expenses. The Prescription Centre database allows the identification of individuals using selected medications of interest.
Register of Primary Health Care Visits(33)	The register covers all outpatient primary health care services delivered in Finland.
NORWAY	
The Emergency Preparedness Register for COVID-19 (34) (consisting of the data sources below)	Data for this study will be obtained through the Emergency preparedness register for covid-19 ("Beredt C19"), which is administered by the Norwegian Institute of Public Health, according to the Norwegian Health Preparedness Act §2-4. The register was established in 2020 to provide authorities with up-to-date information on prevalence, causal relationships, and consequences of the covid-19 epidemic in Norway and includes the total population in Norway. The register includes information already collected in the healthcare system and the national health registries (see the following data sources).
Norwegian Population Register	The register holds information on birthdate, immigration and emigration status as well as and death for all residents of Norway.
State register of employers and employees (NAV AA	The register holds lists of all employment relationships in Norway, and employers and contractors are obliged to report their employees and freelancers to the register. Employees are classified according to the Norwegian Standard Classification of Occupations) and can thus be used to

The Norwegian Information System for the Nursing and Care Sector (IPLOS) (36)	The register holds information on the health care services that are provided by municipalities in Norway. Report of applicants and recipients of such services to the register is mandatory for all municipalities. The register includes information on home care service and out-of-hospital institutional care, including short- and long-term nursing home stay.
The Norwegian Immunisation Register (SYSVAK) (37)	The register holds information of administered vaccines in Norwegian vaccination programs, including the date of administration and type of vaccine. For the covid-19 vaccines, reporting to the register have been mandatory.
Norwegian Surveillance System for Communicable Diseases (MSIS)	The register holds information on selected infectious diseases for which reporting to the register is mandatory. This includes all covid-19 tests and the date of testing and test results.
The Norwegian Patient Registry (NPR) (38)	The register holds information on all contacts with specialist health-care services in Norway, including admission and discharge dates as well as diagnoses (recorded according to ICD-10) during hospitalization or outpatient contact.
SWEDEN	
The Total Population Register (39)	The register contains information on the unique personal identifier for all individuals in Sweden as well as general demographic information such as date of birth, sex, country of birth, place of residence, date of immigration and emigration and date of death. The register is held by Statistics Sweden.
The Longitudinal Integrated Database For Health Insurance And Labour Market Studies (LISA) (40)	The database contains a wide range of socioeconomic information including occupation (such as healthcare worker). The register is held by Statistics Sweden.
Register On Persons In Nursing Homes (41)	The register holds information on nursing care given to elderly and/or persons with physical, psychiatric or intellectual disabilities at either nursing homes, own homes or other institutions. The register is held by the National Board of Health and Welfare.
The National Vaccination Register (42)	The register contains information on administered covid-19 vaccines including data on date of administration, the specific vaccine products,

	substance, formulation, batch number and dose number (for repeated doses) since 1 January 2021. The register is held by the Public Health Agency of Sweden.
Register On Surveillance Of Notifiable Communicable Diseases (Sminet) (43)	The register contains information on notifiable diseases (for which reporting is mandatory) reported by either the analysis performing laboratories, the treating physician or autopsy performing physician, in accordance with the Swedish Communicable Diseases Act. Data include date of disease occurrence, date of testing, date of positive test and diagnoses. The register is held by the Public Health Agency of Sweden.
The Swedish Patient Register (44,45)	The register comprises information on all in-hospital (since 1987) and out- patient (since 2001) specialist care in Sweden including data on admission and discharge dates, whether hospitalization was planned or acute, codes for discharge diagnoses and surgical procedures, whether discharged as deceased, to own private residence or other health care facilities, type of department, and hospital. For the current study period discharge diagnoses were recorded according to the Swedish clinical modification of the ICD-10 (i.e. ICD-10-SE). The register is held by the National Board of Health and Welfare.

9.5 Study size (sample size and power)

We expect the Nordic countries to contribute with 19.6 million individuals vaccinated with at least two doses - based on a combined population of 23.1 million and a vaccination uptake of approximately 85% among individuals aged 12 years or older. The vaccination uptake in the 5to11-year olds will be lower: we expect at least 50% for one dose of vaccine in the countries that have recommended vaccination in this age group. The policy for vaccination 5- to 11-year olds was different in each country: Denmark recommended vaccination of all 5- to 11-year olds, Finland has also offered vaccination, while Norway and Sweden has recommended vaccination of risk groups among the 5- to 11-year olds. In all Nordic countries, the reduced dosage of BNT162b2 in two doses has been used in this age group. The statistical power will depend on the prevalence of the respective schedule being studied and the comparator schedule together with the frequency of the outcomes (PCR positive tests are not uncommon in individuals, while covid-19 hospitalization, ICU admission and deaths will be rarer). The Nordic countries have had similar mass vaccination rollouts with prioritized groups being vaccinated first followed by adult age groups; for both the primary series of 2-doses and for the 3rd booster dose. The two mRNA vaccines and the two viral vector vaccines have been in use in the Nordic countries; the BNT162b2 has been the most used type. The use of the

ChadOx1 viral vector vaccine early in the rollouts did differ between countries, with Denmark, Norway using it for frontline personnel, while Sweden, and Finland used it more generally. After the VITT signal the vaccine was discontinued first in Denmark and later followed by Norway. In Sweden and Finland, the use of the vaccine was initially restricted to 65 years or older after the VITT signal, but later the vaccine was discontinued. The restricted study designs that we will use may also reduce statistical power. However, this is a trade-off in the effort of constructing more comparable groups and, thus, better causal inference. The multi-country nature of our study will increase statistical power, especially for comparisons and outcomes where differences will be difficult to identify for single countries.

9.6 Data management

[figure not shown]
Data management will be conducted at the country-specific level complying with the respective national data security and privacy guidelines. All study subcontractors have access to their country-specific data and can link data between their country's registers for the purpose of our study. Due to the short timeline and resources allocated, data management and analyses will be accomplished at the national level (i.e. one large combined database containing fully anonymized individual-level data for all 4 countries is not feasible). No sensitive data will be shared between partners in this project. Only effect estimates and aggregated data will be shared.

9.7 Statistical analysis

Heterologous vs homologous comparisons – restriction to period- and age overlapping between groups

For the 2- vs 2- and 3- vs 3-dose comparisons (objective #1, heterologous vs homologous), the day the last vaccine was administered in the respective schedules will serve as the index date (see Figure 1 and 2). One main challenge is that vaccination schedules are correlated with age and calendar period. To certify that the vaccination periods (calendar periods where the specific schedule was used) and age intervals are similar between the comparative groups, we will identify the earliest and latest dates and youngest and oldest ages that comprises 95% of the vaccinated individuals in the heterologous schedule under study (i.e. studied schedule). These period- and age-intervals will serve as an eligibility criteria for the homologous comparison schedule vaccinated individuals. That is, to be included in the respective homologous vaccinated comparison schedule cohort, an individual will have to have received their index vaccine dose within the same period- and age-intervals as the heterologous vaccinated, that have received their index vaccine dose outside of the distinctly defined period- and age-95%-

intervals will be excluded from the cohort analysis. Adjustment will be accomplished through use of inverse probability weights – see subsection *Adjusted cumulative incidences* below. We will take the following potential confounders into account, age (5-year bins), calendar month of receiving the 2. or 3. dose (according to the compared schedules), sex, vaccination priority group and comorbidities.

[figure not shown]

[figure not shown]
3-dose vs 2-dose comparisons - restriction through matching

For the 3-dose vs 2-dose comparison (objective #2), we will use a 1-to-1 matched design, similar to previous work (See Figure 3 and 4).(17) The study period will be from the date when rollout of booster doses were initiated, specific for each country (e.g. 6 September 2021 for

Denmark and 17 September 2021 for Finland), and until 28 February 2022 (end of study period).

At the day an individual receives a 3. dose (i.e. the index date) of the studied schedule, the individuals will be matched with an individual having received the respective 2-dose comparison schedule (i.e. controls) but have not yet received a 3. dose (i.e. at the this date). For each matched pair, the index date of the individual in the 3-dose studied schedule will be assigned to the 2-dose comparison schedule control individual. The matched controls will be eligible to be included in a 3-dose studied schedule group in case of receiving a future 3. dose to that of the given matched date. Individuals from the 3-dose studied and the 2-dose comparison schedules will be matched on age (5-year bins), calendar month of receiving the 2. dose and a propensity score summarizing potential confounders such as sex, vaccination priority group and comorbidity. The time at which an individual was vaccinated with a 2. dose, is highly correlated with risk of severe covid-19 and/or risk behavior due to the national prioritization of the rollout of the covid-19 vaccines (e.g. individuals of high risk of severe covid-19 and health care workers were prioritized for earlier vaccination than the general public).

Individuals in the country-specific cohorts will be followed from the time they enter one of the vaccination schedules groups and 13 days have passed until one of the endpoints included in the study, end of endpoint ascertainment period, received a booster dose (a 3. dose for 2-dose schedules and a 4. dose for 3-dose schedules), exit from the cohort due to death, loss to follow-up, emigration, or end of study period, whichever occurs first. I.e. for the 3- vs. 2-dose matched comparisons, follow-up for the matched pairs will also end if the control individual receives a 3. dose (on that date; see example in Figure 4B). Follow-up will be conducted separately for each outcome without censoring for the other study outcomes. That is, when evaluating effectiveness against covid-19 hospitalization to an ICU, having a positive PCR test for SARS-CoV-2 or being covid-19 hospitalized does not right-censor the follow-up for this individual. However, note that when the 14 days and 30 days, respectively, after a positive test has passed, the follow-up will be censored in the analyses of hospitalization and ICU, and mortality, respectively.

[figure not shown]

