We will use comparative designs to evaluate the majority of the objectives; thus, we will avoid comparisons with unvaccinated individuals. This will reduce concerns about bias due to inherent differences in who chooses to remain unvaccinated during the pandemic as well as concerns about healthy vaccinee bias whereby individuals recently vaccinated may be healthier than unvaccinated individuals, since current illness can delay vaccination appointments. This will also reduce concerns about ascertainment bias due to differences in testing behavior between vaccinated and unvaccinated groups. Finally, the research questions at hand are inherently comparative in the real-world setting of a completed mass vaccination rollout. Therefore, it is not a matter of vaccine vs no vaccine, but whether a heterologous schedule is non-inferior to a homologous schedule with respect to comparative VE and whether a third

dose increases VE compared to two doses. Individuals who remain unvaccinated at this point in time, are unlikely to be swayed by further real-world evaluations of effectiveness.

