The endpoints will be: 1) a positive PCR test for SARS-CoV-2 (i.e. infection), 2) a covid-19 hospitalization, 3) covid-19 hospitalization at an intensive care unit (ICU) and 4) covid-19 related death. In the primary analyses we will follow up for the endpoints from start of follow-up defined as day 14 after the index date, and until 75 days have elapsed since the start of follow-up. These outcome ascertainment periods have been chosen to balance: a) that the follow-up among the comparison groups will be homogenous in contrast to longer periods of outcome ascertainment where right censoring at study end or another dose may differ substantially between comparison groups, and b) that we need to have sufficient follow-up for the assessment of hospitalization and mortality. When evaluating waning of immunity, follow-up for endpoints will continue beyond day 75.

Covid-19 hospitalization

Covid-19 hospitalization will be defined as an event fulfilling the following criteria: a) hospitalization with a PCR positive test for SARS-CoV-2 dated in the time period beginning 14 days before admission (day -14; the day of admission is day 0) and up to and including 2 days

after admission (day 2), b) inpatient hospital contact or a hospital contact with a duration of at least 12 hours and c) a covid-19 relevant diagnosis code (ICD-10: B342, B342A, B948A, B972, B972A, B972B, B972B1 or Z038PA1 – subject to country-specific coding practices, see table below - TIME-VARYING VARIABLES). Thus, individuals who are hospitalized for conditions not related to covid-19, but who coincidentally test positive in the period around admission (14 days before to 2 days after admission) will be included as an endpoint 1 (infection) but not an endpoint 2 (hospitalization). An example of this could be a patient with a fracture who test positive at admission as part of routine testing. This distinction is particularly important to make during periods of high incidence of infection as in the period of omicron. Covid-19 hospitalization to an ICU (endpoint 3) will be assessed among those individuals fulfilling the criteria for covid-19 hospitalization (endpoint 2).

Covid-19 related mortality

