Covid-19 related death will be defined as death within 30 days after PCR positive test for SARS-CoV-2. While this definition will allow us to assess the outcome contemporarily (i.e. no lag time) and is an epidemiological standard measure of infection-related mortality, a limitation to this approach is that it does not include covid-19 related death later than 30 days and may include deaths not specifically related to severe covid-19. Potential bias from these limitations, however, are mitigated by use of the comparative design (in which, we would not expect the risk of potential misclassification to be different between comparative groups). Some countries may be able to supplement with information from cause-of-death registers, but the inclusion of this information will be subject to availability.

In secondary analyses, all outcomes will be sub classified according to SARS-CoV-2 variants of concern using either a "periods of dominance"-approach where for each country we have identified the periods where specific variants dominated or, subject to data availability, variant-PCR and WGS results – see subsection *Intended additional analyses* below.

Through use of the planned outcomes, we will be able to provide information on the VE in relation to any SARS-CoV-2 infection as well as severe covid-19. In addition, variant-specific secondary analyses will provide information on VE according to specific variants of concern. The Nordic health care registers do not hold information to distinguish between symptomatic and asymptomatic documented SARS-CoV-2 infection.

COVARIATES

We will take the following potential confounders into account: age (using year of birth), sex, calendar month (of vaccination; ie, the index date) and vaccination priority group (nursing

home residents, healthcare personnel and individuals at risk of severe covid-19 due to comorbidities).

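### In the 3- vs 2-dose comparison, ending pairs at the control's 3rd dose while infected controls stay at risk biases booster VE against hospitalization, ICU and death upward, to the extent that infection defers boosting

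*Protocol*

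**What the plan says.** Section 9.7 of the protocol fixes the relevant rules for objective #2.

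- **Pair exit.** "follow-up for the matched pairs will also end if the control individual receives a 3. dose".
- **Infection does not end follow-up for severe outcomes.** "Follow-up will be conducted separately for each outcome without censoring for the other study outcomes". For ICU admission, for example, "having a positive PCR test for SARS-CoV-2 or being covid-19 hospitalized does not right-censor the follow-up for this individual".
- **A limit after the test.** "when the 14 days and 30 days, respectively, after a positive test has passed, the follow-up will be censored": 14 days for hospitalization and ICU, 30 days for mortality.
- **Estimator.** Comparative VE is 1 minus the ratio of day-75 cumulative incidences in the matched populations. Matching uses age, month of the 2nd dose and a propensity score, all baseline quantities. No weighting for censoring is described.

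Section 9.3 sets the window, from day 14 after the index date "until 75 days have elapsed since the start of follow-up". It links an admission to a positive test from 14 days before to 2 days after admission, and "Covid-19 related death will be defined as death within 30 days after PCR positive test".

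Section 9.2, arguing against unvaccinated comparators, notes that "current illness can delay vaccination appointments". The point is not taken up again for the pair censoring.

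**The concern.** The pair rule looks symmetric because both members leave on the same day. What triggers it is the control's behaviour alone. A control who has just tested positive may put off the 3rd dose, while uninfected controls continue to be boosted and their pairs leave. Among the 2-dose people still under observation, the share recently infected, and so about to be admitted or to die, is then too high. The 3-dose member's exit depends on the partner's boosting and not on that member's own infection, so the 3-dose arm is not enriched in the same way.

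The error runs in one direction: control risk is overstated and booster VE is too high. Objective #2 is primary and asks what a third dose adds. Its study period starts at booster rollout, when controls are being boosted. The two quality-control analyses in Section 9.8 evaluate the infection endpoint only, where the event is the positive test itself, so they cannot show this bias. Section 9.9 does not list it.

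**Working it through.** The protocol states no figure to reproduce. It gives no booster uptake among controls, no distribution of the lag from test to event and no degree of deferral, so all three are assumed below.

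**Assumptions**
- Boosting rate b among uninfected controls: 0.5%, 1%, 2% or 3% per day. The share boosted within 75 days is 1 - (1 - b)^75, that is 31%, 53%, 78% and 90%.
- Lag U from positive test to event: gamma, shape 4, mean 5 days (hospitalization) or 12 days (death).
- Deferral after a positive test: full (no infected control is boosted before the event) or half.

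**Approximation.** Take an event at time t from an infection at t - U. Under full deferral the infected control had to escape boosting only until t - U, while uninfected controls had to escape it until t. The control hazard is therefore inflated by about M = E[exp(bU)] = (1 - b x mean/4)^-4. With a true RR of 1, the apparent VE is 1 - 1/M = 1 - (1 - b x mean/4)^4.

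| b per day | Hospitalization, mean 5 days | Death, mean 12 days |
|---|---|---|
| 0.5% | 1 - 0.99375^4 = 2.5% | 1 - 0.985^4 = 5.9% |
| 1% | 1 - 0.9875^4 = 4.9% | 1 - 0.97^4 = 11.5% |
| 2% | 1 - 0.975^4 = 9.6% | 1 - 0.94^4 = 21.9% |
| 3% | 1 - 0.9625^4 = 14.2% | 1 - 0.91^4 = 31.4% |

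**Simulation.** Matched pairs, infection hazard 0.2% per day, Kaplan-Meier at day 75, with the plan's pair censoring and 14/30-day censoring.

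- True VE 0%, full deferral, b from 0.5% to 3%: RR 0.98 to 0.84 for hospitalization and 0.95 to 0.71 for death. The apparent VE is about 2-16% and 5-29%. The hospitalization figure varies somewhat with the details of the simulation: at 3% per day, separate runs gave RR 0.84 to 0.90.
- True VE 0%, half deferral: about half as much. At b = 2%, with a mean death lag of 14 days, control risk was inflated 1.06-fold (hospitalization) and 1.16-fold (death), against 1.12 and 1.32 with full deferral.
- No deferral: RR 1.00-1.01, which isolates deferral as the cause.
- True VE about 70%, full deferral: the estimate rises by about 1-5 percentage points for hospitalization and 2-10 for death.

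**Interaction with the 14-day limit.** At b = 2%, removing that limit moved the null hospitalization RR from about 0.92 to 0.95. The limit takes infected controls who never become severe out of the denominator, so part of the bias arises from the two rules together.

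**The case against.** The strongest reply is that every driver of the size is assumed. Section 9.2 says only that illness can delay an appointment; it does not say that infected controls are seldom boosted. That stands, and it is why half deferral is shown beside full deferral.

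Constant boosting of 1-3% per day means 53-90% of controls boosted in the window. If the rate instead halves every 20 days (also an assumption, 24-56% boosted), null RRs with full deferral are about 0.99-0.95 for hospitalization and 0.96-0.90 for death. Section 9.3 also accepts tests taken at or just after admission, and these carry no lag. If half of hospitalizations have none, the null RR is about 0.99-0.94, close to simulation noise (about 0.01) at the lower rates. Both stand as reasons why the bias may be small.

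The background in Section 7 reports that a third dose protected against severe outcomes in a large Israeli cohort, so a useless third dose is not the most relevant case. That also stands: near 70% true VE the hospitalization error is a few points.

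A reader might infer that the plan's booster VE against severe disease would be largely artefact, or that objective #2 as a whole is biased. The documents support neither. The primary outcome ends at the positive test and is not touched by this mechanism. Nothing in the protocol establishes full deferral or rapid uptake. Objective #1 has no pair censoring.

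None of this removes the mechanism. The censoring rule, the continued follow-up after a test and the estimator are all fixed in the text, and nothing offsets the resulting dependence.

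**Conclusion.** The concern holds conditionally, for hospitalization, ICU and death in objective #2 only. To the extent that a recent positive test defers boosting, censoring is informative in the 2-dose arm alone and VE is biased upward. The direction follows from the protocol's rules plus that one premise; the size does not. The upper ends of the ranges need boosting near 3% per day and full deferral. The bias is largest for death, because the lag is longer, and smaller with slower boosting or with many tests taken at admission. If uptake differs between countries, the bias would differ too and enter the meta-analysis. The issue deserves a change before analysis but does not undermine the primary endpoint.

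**What to change.** For the severe outcomes in objective #2, apply the censoring at the infection date.

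- Follow each member to that member's own first positive PCR, the control's 3rd dose, day 75 or the other existing exits.
- One member's infection does not end the partner's follow-up. A control's 3rd dose after that control's own positive test does not remove the control's event.
- Count the infection as severe if the admission or ICU admission falls in the Section 9.3 window, or death occurs within 30 days of the test. Estimate its cumulative incidence with other infections as competing events.
- Exclude, in both arms, people who test positive between the index date and day 14.

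In simulation, dating events at the test with competing events returned RR 0.99-1.01 under the null. With a true RR of about 0.52 it returned 0.51-0.52, where the plan's rule gave 0.45-0.48 (hospitalization) and 0.38-0.47 (death) at 1-3% boosting per day.

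Alternatively, keep the current event dates and add inverse-probability-of-censoring weights with time-varying infection status.

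Cost: protocol wording and reprogramming, from the same registers. The estimand of the first option becomes infections by day 75 that turn severe. Accrual must stop 14 or 30 days before 28 February 2022 (14 February or 29 January), or outcome data must run slightly past that date.
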